Dehydration is a serious but preventable complication in patients with new ileostomies. Even small changes in fluid intake or output can cause body fluid imbalances that promote dehydration and necessitate IV rehydration (Messaris, 2012). Previous research has shown that the use of pre-operative teaching, direct patient engagement from post-op day one, engaging patients to perform self-care for their stoma during hospitalization, and having patients track intake and output post-discharge can decrease readmission rates (Nagle, 2012). With implementation of this pathway over the course of 7 months, there was a decrease in the overall 30- day postdischarge readmission rate for patients with new ileostomies from 35.4% to 21.4%, with the rate for dehydration alone falling from 15.5% to 0% (Nagle, 2012).

The Ostom-i alert (OIA) is a discrete novel device which clips onto any ostomy bag from edge to edge and measures the horizontal tension between the edges over time, as a result of stool volume in the ostomy. It is an FDA approved medical device.

Until now, the OIA has been mainly used to warn patients when the ostomy bag is at risk of overflow thereby reducing the risk of leakage causing embarrassment to the patient and caregivers. It can also be used to evaluate the overall output of the ostomy. When patients leave the hospital, the OIA data is sent to the patient's smartphone through bluetooth technology and can be viewed on the internet in real time by the surgical team (stoma nurse, surgeon, clinical research staff). This would allow patients to monitor their output more accurately and allow them to contact clinical staff with questions or to help with bowel management when output is outside of established parameters (too little or too high output).

While all patients with ileostomy have a risk of dehydration, early identification of those at greater risk may lead to home intervention and decreasing hospital readmission. Decreased readmissions ultimately leads to faster post-operative recovery, decreased risk of sequela of readmission (nosocomial infection, pneumonia etc) and decreased healthcare costs.

C. Specific Aims

Study Aims

The aim of the study is to evaluate the efficacy of the Ostom-i device in decreasing readmission rates of subjects in the first 30 days post-operatively.

Hypothesis:

We hypothesize that readmission rates will decrease with use of Ostom-i device.

Primary Outcome:

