Subjects will be monitored until the 30 day post-operative period is completed. Any phone calls to office due to high or low output will be documented. All patients are seen as standard of care by their treating physician and stoma nurses at 4-6 weeks post op. Any readmissions to outside hospitals are documented at the post-op visits.

E. Data Analysis

Intent-to-treat:

While a randomized study design is ideal, due to financial limitations, we are limited to 30 devices and therefore plan to treat a single cohort of 30 patients. The primary analysis outcome will be readmission rate for dehydration, and the analysis of this outcome will utilize an intent-to-treat analysis population including all 30 patients. Established readmissions rates will be used as a historical control group to compare readmission rates. Confounding will be minimized

because subjects will be treated per standard of care in addition to receiving education about the Ostom-i device.

Given previous studies suggesting that more awareness leads to a decrease of admission to 0% (Nagle, 2012), we expect that there will be no more than one readmission among these 30 patients. The study has 90% power to rule out a readmission rate for dehydration $\geq 15\%$ in favor of a significantly reduced rate of $\leq 2\%$ with p ≤ 0.05 by using an exact test.

If the study results appears promising (i.e., no or only one readmission), given the very low risk to patients, a larger scale randomized controlled trial will be considered by requesting additional funding.

F. Potential Benefits and Risks, Monitoring and Quality Assurance

I. Benefits

It is hoped that the OIA device will be able to provide more accurate real-time monitoring of ostomy output that will ultimately reduce readmission rates due to dehydration by allowing better management of fluids and hydration post-operatively. The results of this study may benefit future subjects long-term by allowing subjects access to technology which will influence the post-op treatment of dehydration and fluid imbalance following ileostomy surgery.

II. Risks and discomfort

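### The stated 90% power is not reached at a 2% dehydration readmission rate: the one-sided exact test that the plan implies has 87.9% power with 30 subjects

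*Combined protocol and SAP*

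**What the plan says.** The plan's only power statement is in section E (Data Analysis). It reads "The study has 90% power to rule out a readmission rate for dehydration" of at least 15%, "in favor of a significantly reduced rate of" at most 2%, "with p ≤ 0.05 by using an exact test".

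The other inputs come from the same section:

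- **Endpoint:** "The primary analysis outcome will be readmission rate for dehydration".
- **Analysis set:** an "intent-to-treat analysis population including all 30 patients".
- **Origin of the sample size:** "we are limited to 30 devices and therefore plan to treat a single cohort of 30 patients".
- **Decision rule:** the words "If the study results appears promising (i.e., no or only one readmission" open the condition under which a larger randomised trial would be considered.

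The side of the test is not stated. The 15% null is close to the historical figure in section B (Background/Significance), where an ileostomy pathway is reported "with the rate for dehydration alone falling from 15.5% to 0" percent.

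**The concern.** The sentence fixes the sample size, null rate, alternative rate, significance level and type of test, so the power can be recalculated with a single unknown, the side of the test. An exact test on 30 binary outcomes has few possible rejection regions, and power moves in large steps between them. A power of exactly 90% at 2% is not one of the values available.

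What is at stake is small. A reader who takes the sentence at face value believes that a true 2% rate would be missed 10% of the time, when the figure is 12.1%. The leftover ambiguity about sidedness matters more, because the two readings give very different power.

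**Working it through.** **Inputs.** From section E: n = 30, all analysed; null rate 15%; alternative 2%; level 0.05; exact test; stated power 90%. From section B: historical rate 15.5%. Let X be the number of subjects readmitted for dehydration, X ~ Binomial(30, p).

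**Step 1: rejection region, one-sided.** Find the largest c with P(X ≤ c | p = 0.15) ≤ 0.05.

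- P(X ≤ 0) = 0.85^30 = 0.0076
- P(X ≤ 1) = 0.0076 + 30 × 0.15 × 0.85^29 = 0.0076 + 0.0404 = 0.0480
- P(X ≤ 2) = 0.0480 + 0.1034 = 0.1514

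So the test rejects at 0 or 1, with actual size 0.048. This agrees with the plan's own rule for a promising result.

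**Step 2: power at 2%.**

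P(X ≤ 1 | p = 0.02) = 0.98^30 + 30 × 0.02 × 0.98^29 = 0.5455 + 0.3340 = 0.8795.

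The stated 90% is not reproduced. The gap is 90.0 − 87.9 = 2.1 points, and the chance of missing a true 2% rate is 100 − 87.9 = 12.1%.

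**Step 3: where 90% would hold.** Power of the same rule by true rate:

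| True rate | Power |
|---|---|
| 1% | 96.4% |
| 1.5% | 92.6% |
| 1.79% | 90.0% |
| 2% | 87.9% |

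The alternative is written as a range up to 2%. A power claim over a range has to hold at its least favourable end, which is 2%.

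**Step 4: could another test give 90%?**

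- *Two-sided exact.* One event gives p = 0.076 (0.096 if the tail is doubled), so only X = 0 rejects. Power at 2% is 0.98^30 = 54.5%.
- *Mid-p.* 0.028 at X = 1 and 0.100 at X = 2, so the region and the 87.9% are unchanged.
- *Most powerful level-0.05 test (Neyman-Pearson).* Reject at X ≤ 1, and at X = 2 with probability (0.05 − 0.0480)/0.1034 = 0.0191 (unrounded inputs). Power = 0.8795 + 0.0191 × 0.0988 = 0.8813. No level-0.05 test of 15% against 2% with 30 subjects can exceed this.
- *Null of 15.5%.* P(X ≤ 1) = 0.0416 and P(X ≤ 2) = 0.1351, so the region and power are the same. The ceiling is 0.8795 + [(0.05 − 0.0416)/(0.1351 − 0.0416)] × 0.0988 = 0.8884 (unrounded inputs).

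**Step 5: how close the size is to its limit.** With 29 subjects, P(X ≤ 1 | 0.15) = 0.85^29 + 29 × 0.15 × 0.85^28 = 0.0549, above 0.05. Only X = 0 would then reject, and power at 2% would be 0.98^29 = 55.7%.

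**The case against.** The best defence is rounding. The rates are given in whole percents. The 0-or-1 rule has 90.0% power at 1.79%, which rounds to 2%; an author who solved for the rate detectable with 90% power and rounded it would have written this sentence. Rates that round to 2% run from 1.5% (power 92.6%) to just under 2.5% (0.975^30 + 30 × 0.025 × 0.975^29 = 0.468 + 0.360 = 82.8%), so 90% lies inside that span. Alternatively, 90% may be a loosely rounded 88%. The claim is also true over most of the stated range, from 0 to 1.79%, and the section leans on an earlier study in which the rate fell to 0%. Finally, nothing depends on the difference: the sample size came from the number of devices, and the study is a pilot.

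Part of this stands. The discrepancy is small, it may well have arisen from rounding, and it changes no decision. But the plan shows no working and does not mark the figure as approximate, so the rounding route is a guess. To the nearest percent, 87.9% is 88%. The only alternative rate that the plan names is 2%, and there the claim fails.

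Leaving the side of the test open does not rescue the figure either, because the two-sided reading takes it much further from 90%.

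**Conclusion.** The concern holds, as a minor error. With 30 subjects the implied one-sided exact test has 87.9% power at 2%, not 90%, and no level-0.05 test exceeds 88.1% against a 15% null or 88.8% against 15.5%. The miss probability at 2% is 12.1% rather than 10%.

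This rests on two readings. First, the test is one-sided, which is the reading most favourable to the plan and the only one that rejects at one readmission. Second, all 30 subjects contribute an outcome, as the plan intends. The rule for a promising result does not say that it counts dehydration readmissions only; that is assumed here from the primary outcome, but the power figure does not depend on it, because the critical value comes from the test itself.

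**What to change.** Replace the power sentence in section E with wording such as: *With 30 subjects, a one-sided exact binomial test of H0: dehydration readmission rate ≥ 15% at the 0.05 level rejects if 0 or 1 of 30 is readmitted for dehydration (actual size 0.048); power is 88% if the true rate is 2%.*

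The cost is one sentence and a slightly less favourable figure. Sample size, rejection region and the rule for considering a larger trial are unchanged. The new wording also settles the side of the test and shows how close the size is to 0.05. That is useful to know because section F lets subjects discontinue at any point, and with one fewer evaluable subject a single readmission would no longer be significant.

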To demonstrate a reduction in readmission of patients with new ileostomies.

D. Methodology

I. Subject Selection

All patients over the age of 18 undergoing procedures with new ileostomy creation at MGH will be offered the opportunity to take part in the trial. We plan to recruit 30 subjects for Ostomimonitoring. Once subjects have consented to participate in the trial, they will be educated about the use of the OIA device and smartphone application as well as the discharge instructions. Specific eligibility criteria for participation in the study include: greater than 18 years of age, English speaking, creation of new ileostomy, access to smartphone with bluetooth technology to support OIA application, and must be able to give written consent.

II. Subject Enrollment

All patients who undergo new ileostomy creation at MGH first meet with the ostomy nurses preoperatively, for an educational session and stoma marking, as per standard of care. All patients scheduled to undergo ileostomies will be offered the opportunity to participate in the study by research nurses. If patients are interested in participating in the study, they will be approached again 24 hours after their surgery, during their first stoma teaching session. Those who wish to participate will be offered the opportunity to ask any questions about the protocol and then sign consent. We will have a total of 30 subjects enrolled and using the device.

III. Study Procedures

Once appropriate IRB approved consent has been given, subjects will be given device and assisted in setting up the OIA app. They will be given education about parameters for ostomy output. All subjects will have additional teaching of specific monitoring parameters and education about the device.

Once subjects are trained on the device, they will monitor outputs on a daily basis including during initial hospitalization until 30 days post-op. Outputs will be recorded by the Ostom-i application, which will be shared via bluetooth technology with the surgeon and research nurses in real time. If outputs are less than 250mL or greater than 1200mL per day, subjects will be alerted by system and subjects will be instructed to call their surgeons who will adjust their medications and fluids accordingly.

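### The 15% null in Section E has no stated source and may not be the site's rate under its existing stoma teaching, so 0 or 1 readmission in 30 need not reflect the device

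*Combined protocol and SAP*

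**What the plan says.** Section E (Data Analysis, Intent-to-treat) plans one cohort of 30 patients, with dehydration readmission as the primary analysis outcome and unspecified established rates as the historical control. It states: "The study has 90% power to rule out a readmission rate for dehydration" of at least 15%, in favour of a rate of at most 2%, "with p ≤ 0.05 by using an exact test". No or one readmission is called promising and would lead the team to consider a randomized trial. The section also argues that confounding is minimized because patients receive standard of care plus education about the device.

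Section B (Background/Significance) describes a cited study of a teaching pathway. Its components were "the use of pre-operative teaching, direct patient engagement from post-op day one", stoma self-care in hospital, and patient tracking of intake and output after discharge. Readmissions fell after it was introduced, "with the rate for dehydration alone falling from 15.5% to 0" per cent.

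Section D.II (Subject Enrollment) says that all new-ileostomy patients at the site see the ostomy nurses before surgery "for an educational session and stoma marking, as per standard of care". Of those interested in the study it says "they will be approached again 24 hours after their surgery, during their first stoma teaching session". Consent is signed after that approach.

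**The concern.** A single-arm test against a fixed rate is a test of the device only if that rate is what these patients would have had without it. Section E does not say where 15% comes from. The one nearby figure in the document was recorded before a teaching pathway, and the site already gives every eligible patient at least one element of that kind of teaching. If this teaching holds the site's rate below 15%, the trial can reject 15% with a device that does nothing.

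Standard of care then does not minimize confounding, as Section E claims. It is itself a possible explanation of a low count. Section D.III adds further study teaching on output parameters, given together with the device. At stake is the stated aim, device efficacy, and the decision to seek funding for a randomized trial.

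**Working it through.** **Inputs.** From Section E: n = 30, null 15%, alternative 2%, p ≤ 0.05 by an exact test, promising if X ≤ 1, stated power 90%. From Section B: dehydration readmission 15.5% before the pathway and 0% after. The site's own dehydration readmission rate without the device is not given, so every background rate p below is an assumption.

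**Formula.** P(X ≤ 1) = (1 − p)^30 + 30·p·(1 − p)^29.

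**The plan's own figures.**
- Error at p = 0.15: 0.0076 + 0.0404 = 0.0480, one-sided.
- Power at p = 0.02: 0.5455 + 0.3340 = 0.8795, so about 88% rather than the stated 90%. Nothing below depends on this gap.
- The test has to be one-sided. One readmission in 30 against 15% gives a two-sided p of 0.076 (minimum-likelihood method), which would not meet 0.05.

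**Where 15% could come from.** The rates in the document are:
- dehydration, new ileostomy: 15.5% before the pathway and 0% after;
- all-cause, new ileostomy: 35.4% before and 21.4% after;
- all-cause, colectomy: 11.3% and 10.9% at the site, 13.2% and 10.7% nationally.

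Only the pre-pathway 15.5% is both specific to dehydration and close to 15%. The match is by value; Section E does not state it.

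**Chance of a promising result if the device does nothing.**

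| Assumed background rate | P(0 or 1 in 30) |
|---|---|
| 20% | 0.0012 + 0.0093 = 1.1% |
| 15.5% | 4.2% |
| 15% | 4.8% |
| 10% | 0.0424 + 0.1413 = 18.4% |
| 5% | 0.2146 + 0.3389 = 55.4% |
| 2% | 87.9% |

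**Sensitivity of the rejection count.** The one-sided 95% exact upper limit is 14.9% for 1/30 and 9.5% for 0/30. The 0-or-1 rule is therefore valid at 15% by a narrow margin. For a null between about 9.5% and 14.9%, only 0/30 rejects. For a null below about 9.5%, no result in 30 patients rejects. At a 10% null, 0/30 gives p = 0.90^30 = 0.042, with power 0.98^30 = 54.5% at 2%. At a 5% null, 0/30 gives p = 0.95^30 = 0.215.

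**The case against.** A reader might infer that the 15.5% patients had none of the teaching the site gives, so that the null belongs to a population these patients are known not to be in. The document does not support that. Section B reports the fall with the pathway and does not say what teaching was given before it; an ordinary ostomy-nurse visit may have been part of care there too.

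A reader might also infer that two of the four pathway components are established as routine at the site. Only the pre-operative session is labelled standard of care. The 24-hour session is mentioned in a sentence about interested patients. Because it comes before consent and is called their first stoma teaching session, it is probably routine, but that is an inference, and so is equating it with engagement from the first post-operative day. Nothing shows in-hospital self-care or intake and output tracking to be usual care. Output measurement is what the device supplies, and Section F.II names it as the exception to standard care.

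Nor do the cited before and after rates bound the site's rate. It could exceed 15.5%, and at 20% the rule is conservative. The document gives no reason to prefer 5% or 2%, where the largest figures arise.

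Finally, the plan concedes that randomization would be ideal, cites a limit of 30 devices, and says only that a randomized trial will be considered. Such a trial could separate the device from the teaching.

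All of this limits the size of the claim. It does not supply a source for 15%, and it does not make standard of care a safeguard against confounding when that care includes teaching of the kind Section B credits with lowering readmissions.

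**Conclusion.** The concern holds in limited form. The 15% null is unsourced, and the document gives reason to doubt that it is the site's rate without the device. The 4.8% one-sided error is correct only if that rate is 15%. Across assumed rates from 20% down to 2%, a device with no effect would produce a promising result with probability from about 1% to 88%. The true value cannot be placed in that range from the document. How much existing teaching lowers the rate, if at all, is also unknown.

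The conclusion rests on two inferences: that 15% was taken from the cited 15.5%, and that the 24-hour session is routine. If the second fails, the pre-operative session alone, which is expressly standard of care, still leaves the null unjustified. As written, the plan could credit the device with an effect of teaching the site already gives.

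**What to change.** In Section E, state the source of the null and take it from the 30-day post-operative dehydration readmission rate in the site's own recent new-ileostomy patients under current teaching. Use existing records and apply the trial's eligibility criteria (age, English-speaking, new ileostomy, smartphone access) as far as the records allow. Restate the rejection count and power against that rate.

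The work is a retrospective look-up and revised wording, with no extra patients, but the loss of power may be large and should be stated openly. At a site rate of 10%, only 0/30 rejects and power at 2% is 54.5%. At 5%, even 0/30 does not reject. In that case the study should be reported as an estimate with an exact confidence interval; the two-sided 95% upper limit would be 11.6% for 0/30 and 17.2% for 1/30. A higher site rate would help: at 20%, P(X = 2) = 435 × 0.20² × 0.80^28 = 0.0337, so P(X ≤ 2) = 0.0105 + 0.0337 = 0.0442, and two readmissions would still reject.

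If the site rate cannot be obtained, label 15% as a cited pre-pathway rate (once the sponsor confirms that source), remove the statement that standard of care minimizes confounding, and limit the conclusion to current teaching plus device being below 15%, with no claim about the device alone. That costs only wording.
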